##### 2. Secondary Objectives

- The area of lesions will be obtained from the tracings of the mark obtained by placing a transparent TegaDerm™ adhesive dressing over the mark, removing it (with ink transferred) and pasting on to squared graph paper and then counting the number of squares inside the traced borders.

- The area of the surgical defect will be obtained by placing OpSite™ squared adhesive dressing over the defect prior to commencement of repair, using an ink marker to trace the defect on the dressing, and then counting the number of squares inside the traced borders.
  
- The following will be calculated
  - i. The mean, r.m.s. and maximum difference between the area of the OCT map made by Mohs surgeon and the area of the OCT map made by Observer #1, for lesions in the OCT Arm
  - ii. The mean, r.m.s. and maximum difference of the area of the OCT map made by Observer #1 and the area of final surgical lesion in the Control Arm.

From (i) we will quantify the difference between the Mohs surgeon and Observer's OCT mapping, and whether the Mohs surgeon's margins are consistently smaller or larger.

From (ii) we will determine whether the Observer's margins are smaller or larger than the final surgical lesion, and from (i) then show whether the surgeon's margin are expected to be smaller than the final surgical lesion, and by how much.

Figure 2. Schematic of process showing the areas.

Finally, the average time taken to OCT map lesions will be calculated:

- For all lesions
- For lesions, divided into the following subcategories by clinically visible lesion size:
  - o < 2.0 cm^2
  - o 2.0 – 4.0 cm^2
  - o > 4.0 cm^2

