#### Secondary Objectives:

- Validate that the reduction in MMS stages by use of OCT mapping does not result in an increase in the size of the surgical defect
- Show that the average time taken to perform OCT margin mapping is  $< 5$  minutes for lesions of area  $< 2 \text{ cm}^2$

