#### Avoiding Bias:

The initial OCT mapping, prior to randomization, by another Observer who is not the surgeon, is to detect any bias on behalf of the surgeon who might consciously or unconsciously increase the size of the excision in the OCT Arm (therefore unnecessarily increasing the amount of healthy tissue excised) in order to reduce the number of MMS stages. This first Observer does not know which Arm the patient will end up in and so will simply do their best to map the tumour as accurately as possible. It is then straightforward to compare their results (size of mapped margins) with the surgeon's to confirm the absence of any bias. Their OCT mapping results will also be compared with the size of the final surgical defect (for all lesions) to confirm that (as in all previous studies) OCT mapped borders are no larger than the final surgical defect by conventional MMS.

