#### Study-related interventions

The OCT device is CE marked and has been on the market in first and second generations since 2011. A methodology for using OCT to map the lesion margins has been developed since 2011 and results published [refs] and then further optimized.

The study involves manual measurement of the lesion at 3 stages (on clinical assessment, after OCT mapping, and after surgery). The measurement procedure is very simple and involves placing transparent squared paper over the lesion and tracing the extent. This procedure is a well-established technique for measuring the extent of wounds

In the OCT arm of the study, the Mohs surgeon will make a first incision using the marked OCT margins as the first estimation of the tumour border.

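### The listed area calculations never use the OCT-arm surgical defect, and they contradict the all-lesions comparison promised under Avoiding Bias

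*Protocol*

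**What the plan says.** The Secondary Objectives ask for confirmation that using OCT to save stages "does not result in an increase in the size of the surgical defect". Study Design gives the same aim in terms of tissue excised.

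Avoiding Bias names the threat: the surgeon, "who might consciously or unconsciously increase the size of the excision in the OCT Arm". It offers two safeguards:

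- Observer #1's map is set against the surgeon's: "It is then straightforward to compare their results (size of mapped margins) with the" surgeon's own.
- Observer #1's map is set against the defect: "Their OCT mapping results will also be compared with the size of the final surgical defect (for all lesions" in the study), in order to confirm that "OCT mapped borders are no larger than the final surgical defect by conventional MMS".

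Data and Analysis, 2. Secondary Objectives then lists the calculations. Calculation (i) is the difference between the surgeon's map and Observer #1's map in the OCT Arm. Calculation (ii) is the difference between the map "made by Observer #1 and the area of final surgical lesion in the Control Arm". From the two together the protocol intends to show whether the surgeon's "margin are expected to be smaller than the final surgical lesion, and by how much".

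On how the map guides surgery, Study-related interventions says the surgeon "will make a first incision using the marked OCT margins as the first estimation of the tumour border". Under Final Observations, the defect is measured in every lesion.

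**The concern.** There are two faults. First, Avoiding Bias and Data and Analysis give different populations for the same comparison: all lesions in one, Control Arm only in the other. An analyst cannot follow both.

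Second, the objective is about the hole left after surgery, but the listed calculations end at the line drawn before surgery. The OCT-arm defect, which is the quantity the objective names, appears in neither (i) nor (ii). Taking a wider first layer is the obvious way to bring the stage count down artificially, and the protocol itself identifies this risk. If the section is followed as written, a question about defect size is answered with a statement about map size, and the claim that the saving in stages cost no extra tissue has no direct evidence behind it.

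**Working it through.** The protocol gives no figure to reproduce on this point, so the check is algebra followed by an illustration.

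**Notation.** O is the area of Observer #1's map (all lesions, before randomisation). S is the area of the surgeon's map (OCT Arm only). D is the final defect area (all lesions).

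**What the list estimates**

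- (i) = E[S − O | OCT]
- (ii) = E[O − D | Control]
- Randomisation makes E[O] equal in the two arms, so (i) + (ii) = E[S | OCT] − E[D | Control].

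**What the objective needs**

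- E[D | OCT] − E[D | Control] = (i) + (ii) + E[D − S | OCT].

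Neither calculation supplies the last term, and the protocol does not make it zero. The mark is only the first-stage estimate, and nothing ties the cut exactly to it. The assumed OCT-arm mean of 1.2 stages (Case Number Estimation) is above 1, so some lesions are expected to need excision beyond the first layer.

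**Example with assumed areas.** Suppose S and O agree on average, so (i) = 0.0 cm², and Control defects exceed the map by 0.3 cm², so (ii) = −0.3 cm².

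| E[D − S, OCT] (cm²) | (i) + (ii) (cm²) | True OCT − Control defect (cm²) |
|---|---|---|
| 0.0 | −0.3 | −0.3 |
| 0.3 | −0.3 | 0.0 |
| 0.6 | −0.3 | +0.3 |

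The listed results are the same whether the OCT-arm defect is smaller, equal or larger.

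**Possible size.** The protocol gives no excision width, so these inputs are assumptions. Take a circular map of area A with the cut w beyond the mark: D = π(√(A/π) + w)². The ratio of defect areas when the OCT-arm cut is 1 mm wider than usual is:

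| Usual cut | 0.5 cm² | 1 cm² | 2 cm² | 4 cm² | 6 cm² |
|---|---|---|---|---|---|
| 0 mm | 1.56 | 1.39 | 1.27 | 1.19 | 1.15 |
| 2 mm | 1.36 | 1.28 | 1.21 | 1.16 | 1.13 |
| 4 mm | 1.27 | 1.22 | 1.17 | 1.14 | 1.12 |

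For example, with A = 1 cm² and a usual cut of 0 mm, the radius is 0.564 cm and (0.664/0.564)² = 1.39. With a cut 0.5 mm wider the smallest ratio is 1.06 (4 mm, 6 cm²). The full range is therefore 6% to 56%, and 11% to 39% at 1 cm². The 6 cm² column is only an assumed upper end: the exclusion criterion caps the area of the BCC, not of the map.

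**Does the all-lesions comparison close the gap?** Only if it is reported by arm. The Control mean of (O − D) minus the OCT mean of (O − D) equals E[D | OCT] − E[D | Control], which is the quantity wanted. Pooled over all lesions, it cannot separate the arms. If the stated criterion (map no larger than defect) were applied to OCT-arm lesions, it would become easier to meet as the cut widened, so it could not flag over-excision.

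**Precision of a direct comparison.** With 100 per arm, the half-width of the 95% CI for the log ratio of defect areas is 1.96 × SD × √(2/100). The log-scale SD is assumed.

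| Log-SD | Half-width | CI around the ratio |
|---|---|---|
| 0.3 | 0.083 | −8% / +9% |
| 0.5 | 0.139 | −13% / +15% |
| 0.8 | 0.222 | −20% / +25% |
| 1.0 | 0.277 | −24% / +32% |

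**The case against.** The strongest defence is that Avoiding Bias frames its criterion in terms of conventional MMS, which only the Control Arm receives. On that reading, calculation (ii) does what was meant and the reference to all lesions is loose wording. This explains why Control is the natural reference, but the same sentence still says all lesions, so the conflict remains. It does weaken any criticism that assumes the criterion is applied to OCT-arm lesions, and the finding does not depend on that.

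A second defence is that (i) would expose a surgeon who inflates the map, and that surgery is directed to start from the mark. This is true, and if the final defect always followed the mark, (i) would largely serve. It cannot see cutting beyond the mark or tissue taken at later stages. The illustration does assume such widening; nothing in the protocol shows that it will occur.

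A third is that a between-arm comparison of a secondary endpoint can be left to a statistical analysis plan, which may exist and was not available. That would be fair if the protocol were silent. Instead it specifies both the calculations and the inference, and that inference does not reach the objective.

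Finally, running (ii) in both arms and reporting it by arm already gives the missing contrast. That is correct, and it supports the remedy. Figure 2, a schematic of the areas, was not visible in the text examined. It may clarify intent, but it would not remove the conflict in wording.

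**Conclusion.** The point holds and should be fixed. The scope conflict between Avoiding Bias and Data and Analysis is plain from the text. So is the mismatch between an objective about defect size and an inference about the surgeon's mapped margin. By the identity above, the listed results do not move with the OCT-arm defect when the maps are unchanged; this needs no numerical assumption. The 6% to 56% range shows only what could go unseen. It rests on assumed circular maps of 0.5 to 6 cm², usual cuts of 0 to 4 mm beyond the mark and widening of 0.5 to 1 mm. The estimate of mean stages is unaffected, and the data needed are collected. The fault lies in the analysis list and bears on a secondary objective.

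**What to change.** In Data and Analysis, 2. Secondary Objectives:

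- Calculate (ii) in both arms and report it by arm, and align the wording with Avoiding Bias.
- Add a direct comparison of final surgical defect area between the randomised arms with a 95% confidence interval, and base the conclusion on defect size on that interval.
- Keep (i) as a descriptive check on the drawn map.

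A log-scale ratio adjusted for Observer #1's pre-randomisation map area would be a suitable form and can be left to the statistical analysis plan. Whether to set a margin, and at what value, is for the sponsor to decide.

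The cost is one additional analysis and a wording change. Observer #1's map and the final defect are already measured for every lesion, so no new patients or measurements are needed.

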#### Study Design:

Interventional Randomised Controlled Trial (RCT)

Previously published research [1-5] has shown that, under controlled conditions, OCT mapping of BCC margins is more accurate than clinical assessment and so is expected to produce a reduction in the number of MMS stages. However, the efficiency of the technique, in terms of the reduction in MMS stages versus the additional time required to OCT map the lesion, has not been quantified.

This RCT is designed to quantify the improvement in efficiency, and validate that it is more efficient than standard MMS. The study comprises two Arms, one is the OCT arm and one is the Control Arm. In the OCT Arm, OCT is used to map the tumour margins and the resulting number of MMS stages is recorded.

In the Control Arm, standard MMS is performed.

In order to be completely sure that the reduction in MMS stages using OCT has not been obtained at the cost of increasing the amount of tissue excised, all tumours are also mapped at initial consultation, prior to randomization, by a second observer. See Figure 1 Outline Protocol below.

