#### Figure 1. Outline Protocol

##### Initial Steps

1. Informed consent is obtained from eligible patients
2. Observer #1 (not the surgeon) maps the extent of the BCC tumour using OCT. The time taken, size and shape of the mapped border is recorded.
3. The OCT marks are removed and the patient is asked to return at a later date for the surgical procedure
4. Patients are randomized into two groups, A. OCT Arm and B. Control Arm

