##### A. OCT Arm

5. Observer #2 (the Mohs surgeon) maps the extent of the BCC tumour using OCT. The time taken, size and shape of the mapped border is recorded.
6. The Mohs surgeon performs Mohs surgery using the marked OCT mapped borders as the first stage estimate. The number of MMS stages is recorded.

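### Comparison (i) cannot separate the surgeon's mapping from change in the lesion between visits, so read alone it cannot show that the surgeon was unbiased

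*Protocol*

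**What the plan says.** Under Study Design, "all tumours are also mapped at initial consultation, prior to randomization, by a second observer". The Outline Protocol labels this person Observer #1: "Observer #1 (not the surgeon) maps the extent of the BCC tumour using OCT". It then says: "The OCT marks are removed and the patient is asked to return at a later date for the surgical procedure". Randomisation follows. In the OCT Arm, "Observer #2 (the Mohs surgeon) maps the extent of the BCC tumour using OCT", and next "The Mohs surgeon performs Mohs surgery using the marked OCT mapped borders as the first stage estimate". The Control Arm goes to standard Mohs surgery with no further OCT map.

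Data and Analysis, Secondary Objectives, defines two comparisons:

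- (i), restricted to the OCT Arm, summarises the "difference between the area of the OCT map made by Mohs surgeon and the area of the OCT map made by Observer #1" by its average, root-mean-square and largest value.
- (ii) sets Observer #1's map against the final defect, in the Control Arm only.

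Of (i) the section says: "From (i) we will quantify the difference between the Mohs surgeon and Observer's OCT mapping". It then chains (i) with (ii) to judge the surgeon's margin against the final defect. The Avoiding Bias section uses the surgeon-observer comparison "to confirm the absence of any bias". The same section also intends to compare Observer #1's maps with the final defect in every lesion, not only in controls.

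**The concern.** In (i), mapper and visit coincide completely: the observer comes first and the surgeon later, in every pair. Any real change in the OCT extent of the lesion between the two visits enters the difference with full weight and is read as a property of the surgeon.

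Avoiding Bias presents this check as the means of detecting a surgeon who enlarges the OCT-arm excision to save stages. Two wrong readings are possible. Net growth between visits would look like enlargement by the surgeon. Net shrinkage would offset a real enlargement. Comparison (ii) sets an early map against a late defect, so growth there would favour the expected finding that mapped borders do not exceed the defect.

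**Working it through.** No figure in the protocol bears on this point, so there is none to reproduce. The check is whether the quantity of interest can be identified, followed by an illustration of size.

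**Timing.** Observer #1's map is placed at the initial consultation (Study Design; Initial Steps). That the surgeon's map belongs to the surgical visit follows from the order of the steps and from the surgeon operating on those marks; no separate sentence says so. No interval or maximum interval is given. Observer #1 does not remap at surgery, and controls have no second OCT map. Study-related Interventions also lists a tracing at clinical assessment, but does not say that it is repeated at a second visit. No listed measurement therefore isolates change between visits.

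**Comparison (i) alone.** Observed area ratio = (1 + surgeon effect) × (1 + lesion change). One ratio cannot give two unknowns:

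| Surgeon effect | Lesion change | Seen in (i) |
|---|---|---|
| 0% | +10% | +10% |
| +10% | 0% | +10% |
| +10% | −10% | 1.10 × 0.90 − 1 = −1% |

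The first two rows look the same, and the third hides a real enlargement.

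**Size, under assumed shifts.** For a circular lesion of 1 cm² the radius is √(100/π) = 5.64 mm. A uniform outward border shift d changes the area by ((5.64 + d)/5.64)² − 1:

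- d = 0.1 mm: 3.6%
- d = 0.25 mm: 9.1%
- d = 0.5 mm: 18.5%

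At d = 0.25 mm the change is about 13% for a 0.5 cm² lesion and about 4% at the 6 cm² eligibility limit.

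**Against sampling error.** Assume a between-map SD of 0.3 on the log scale, with 100 pairs (the planned OCT Arm). The standard error is 0.3/√100 = 0.03 and the 95% half-width is 1.96 × 0.03 = 0.059, or about 6%. A 10% change alone would give ln(1.10)/0.03 = 3.18 standard errors. This shows what would happen if a change of that size occurred; it is not evidence that one does.

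**The chain of (i) and (ii).** Let S be the surgeon's map (late), O Observer #1's map (early), D the Control-Arm defect (late) and g the mean change in lesion area between visits. Let O′ = O + g be the map that Observer #1 would have made on the day of surgery. In mean areas:

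- (i) = S − O = (S − O′) + g
- (ii) = O − D = (O′ − D) − g
- (i) + (ii) = (S − O′) + (O′ − D) = S − D

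So g drops out. For a 1 cm² lesion and a 0.25 mm shift, (i) moves by +0.091 cm², (ii) by −0.091 cm², and their sum by 0. This needs g to be equal in the two arms, which randomisation gives in expectation if return intervals are similar. It applies to means, not to the r.m.s. or maximum differences.

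**Regression to zero days.** One could regress the log ratio on the interval and read the intercept as the surgeon effect. With mean interval m and SD s, the intercept's standard error is (σ/√n) × √(1 + m²/s²). If s = m/2, the factor is √5 = 2.24, and the half-width rises from 0.059 to about 0.13. That exceeds ln(1.10) = 0.095, so the intercept could not resolve a 10% effect.

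**The case against.** The strongest reply is that the protocol does not stop at (i). It chains (i) with (ii), and a change common to both arms cancels there on average. This stands. A reader might infer that the lag also undermines the chained conclusion; for mean areas it does not. What remains exposed is each comparison read alone, and the protocol does read (i) alone, in Avoiding Bias and in the Secondary Objectives analysis.

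Second, the magnitude is wholly assumed. The protocol gives no interval, growth rate or between-map SD, and with a short interval and stable lesions the effect may be negligible. This also stands. A reader might infer from the calculation above that (i) will show a false surgeon effect; the documents do not support that.

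Third, growth in an untreated tumour produces only a false alarm in (i), which is conservative for a check against enlargement. This is correct. Masking requires net shrinkage. One might suppose that the biopsy site settles, but the protocol says only that lesions are biopsy-proven and gives no biopsy date. Masking is therefore possible but not shown.

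Fourth, (i) is not the only safeguard. The final defect is measured in all lesions, and every lesion has a map made before randomisation, so a comparison free of the lag in expectation can be made from data already collected. This stands and supplies the better remedy. The listed analyses, however, restrict the defect comparison to controls.

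Finally, the matter might be left to a statistical analysis plan. In part it could be, but the protocol itself fixes the visits, the comparison and its interpretation, and it does not list the interval between maps among the data recorded with each map.

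**Conclusion.** The point holds in limited form. Mapper and visit are fully confounded in (i), so (i) alone estimates the surgeon-observer difference plus any change between visits and cannot establish that the surgeon was unbiased. Comparison (ii) alone carries the same lag with the opposite sign.

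The size cannot be determined from the documents. The 3.6% to 18.5% range for a 1 cm² lesion rests on assumed border shifts and a circular shape, and the comparison with sampling error also rests on an assumed log SD of 0.3. With no change between visits, timing does not distort (i) at all.

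The chained estimate on mean areas is protected, provided that return intervals are similar in the two arms. The primary endpoint, the number of MMS stages, is unaffected. This is an overstated reading of a secondary safeguard and is cheap to correct.

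**What to change.** 1. Record the date of each OCT map and of surgery. Show (i) and (ii) against the interval as a sensitivity display. Do not make a zero-day intercept the main estimate: every patient returns later, so it extrapolates beyond the data, over intervals that were not randomised.
2. In Avoiding Bias and in the Secondary Objectives analysis, describe (i) as the surgeon-observer difference plus any change between visits, and remove the statement that it confirms there is no bias.
3. Base the bias conclusion on final defect area relative to Observer #1's pre-randomisation map, computed in both arms and compared between arms with a 95% confidence interval. Report the chained (i) + (ii) estimate beside it. This also reconciles Avoiding Bias, which covers all lesions, with (ii), which covers only controls. The contrast addresses the first secondary objective directly: whether OCT mapping enlarges the defect. It does not isolate the surgeon's mapping as such.

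The cost is a few dates on the case report form, slightly more analysis and a less categorical statement about (i). The between-arm contrast assumes similar return intervals in the two arms, which the recorded dates allow to be checked.

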### 3. Tertiary Objectives

The results for all lesions in the OCT arm which took more than 1 MMS stage will be analysed as follows:

Calculate the proportions of each BCC subtype (nodular, superficial, or infiltrative BCC, or other) as a % of the total

Calculate the proportion for which the first surgery stage had margins that were not clear (i) laterally (ii) in depth (iii) both

Calculate the proportions of lesions in each of the following anatomical locations: nose, periocular, perioral, ear, other facial location, neck, trunk, limbs.

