#### Tertiary Objectives:

- For those lesions for which OCT margin mapping did not result in a single stage operation:
  - o Determine the proportion of each BCC subtype (nodular, superficial, or infiltrative BCC)
  - o Determine the proportion for which the first surgery stage had margins that were not clear (i) laterally (ii) in depth
  - o Determine whether anatomical location is a factor

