##### Final Observations

8. Finally, prior to closure of the wound, the size of the surgical defect of all lesions is measured by tracing the extent on squared transparent paper and also photographed with a scale. The subtype of the BCC from the Mohs histology is recorded (nodular / superficial / infiltrative / other)

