#### Case Number Estimation:

N=200 patients will be included in the study (100 in each arm).

According to published literature, the average number of MMS stages per lesion is in the range 1.5 to 1.7 [6]. Previous studies with small numbers of patients in non-RCT conditions indicate that presurgical margin mapping with OCT reduces the average number of stages to approximately 1.2 [1-5]. Analysis by a qualified statistician has shown that assuming the true value is 1.2, then 83 patients in the OCT arm will be sufficient to show that the average number of MMS stages is  $< 1.4$  with a confidence level of 95% ( $P < 0.025$ ). This study will be performed with 100 patients in each arm in order to exceed this criterion and show that OCT mapping improves on standard MMS with 1.5 – 1.7 stages.

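### Tabulating location only among OCT-arm lesions that needed more than one stage cannot show whether anatomical location is a factor

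*Protocol*

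**What the plan says.** The Tertiary Objectives in the protocol's Objectives section share one lead-in, "For those lesions for which OCT margin mapping did not result in a single stage operation", followed by three items. The first two ask for proportions: of each BCC subtype, and of first stages with unclear lateral or deep margins. The third is phrased differently: "Determine whether anatomical location is a factor".

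Data and Analysis, 3. Tertiary Objectives, fixes the analysis set: "The results for all lesions in the OCT arm which took more than 1 MMS stage will be analysed as follows". For location, the statistic is "Calculate the proportions of lesions in each of the following anatomical locations: nose, periocular, perioral, ear, other facial location, neck, trunk, limbs". The protocol gives no location distribution for single-stage lesions, no multi-stage rate by location and no comparison group for this item.

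Case Number Estimation gives the scale: "N=200 patients will be included in the study (100 in each arm", and a sample size derived "assuming the true value is 1.2" for the mean number of stages in the OCT arm.

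**The concern.** Asking whether location is a factor is a question of association: does the chance of needing more than one stage differ between sites? That requires the probability of more than one stage given location. The planned table gives the reverse, the probability of each location given more than one stage, which depends on how common each site is among the lesions treated.

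The Rationale says that head and neck sites are the most commonly affected. A large facial share among multi-stage lesions is therefore to be expected even if location has no effect, and a reader could mistake it for one. What is at stake is one stated objective that the planned output cannot answer. The subtype and margin items do not have this problem, because the objectives ask only for proportions there and the analysis delivers them.

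**Working it through.** The protocol states no figure for this item, so there is none to reproduce. The check takes the expected number of events from the protocol and then asks what the planned table can distinguish.

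**Inputs from the protocol.** OCT arm n = 100 and assumed mean 1.2 stages (Case Number Estimation); 8 location categories (Data and Analysis, 3. Tertiary Objectives). The protocol gives no location mix, so the nasal counts below are assumptions.

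**Expected number of multi-stage lesions.** Every lesion has at least one stage, so mean − 1 = expected extra stages ≥ P(more than 1 stage).
- Upper bound: P ≤ 1.2 − 1 = 0.20, so at most 20 of 100 are expected. The bound is reached if no lesion needs more than two stages.
- If the stage count is geometric (assumption): P = 1 − 1/1.2 = 0.167, about 17 of 100.
- The 20 is an expectation and not a cap: the central 95% range of a Binomial(100, 0.20) is 12 to 28.
- Average per category: 17/8 = 2.1 to 20/8 = 2.5 lesions.

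**What the planned table determines.** Write M for more than one stage and L for a location. By Bayes' rule, P(L | M) = P(M | L) × P(L) / P(M). The plan reports the left-hand side. Without P(L), the location mix of all OCT-arm lesions, P(M | L) cannot be recovered.

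**Illustration.** Hold the planned output fixed at 8 of 20 multi-stage lesions on the nose (40%) and vary only the assumed number of nasal lesions among the 100. Brackets are Wilson 95% intervals.

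| Nasal lesions | Multi-stage, nose | Multi-stage, elsewhere | Risk ratio |
|---|---|---|---|
| 20 | 8/20 = 40% (22–61%) | 12/80 = 15% (9–24%) | 2.67 |
| 40 | 8/40 = 20% (10–35%) | 12/60 = 20% (12–32%) | 1.00 |
| 60 | 8/60 = 13% (7–24%) | 12/40 = 30% (18–45%) | 0.44 |

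The planned table is identical in all three rows.

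**Second set of counts.** Fix 10 of 20 multi-stage lesions on the nose (50%) and use odds ratios:
- 20 nasal: (10/10)/(10/70) = 7.0
- 50 nasal: (10/40)/(10/40) = 1.0
- 70 nasal: (10/60)/(10/20) = 0.33

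With 17 multi-stage lesions, 8 of them nasal, the same three totals give (8/12)/(9/71) = 5.3, (8/42)/(9/41) = 0.87 and (8/62)/(9/21) = 0.30. The conclusion does not depend on the counts chosen.

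**The case against.** The strongest reply is that the analysis follows the objective. The lead-in already restricts all three items to multi-stage lesions, two of the three are plainly descriptive, and the third could be read as a loose way of asking where the failures occurred. It is true that the difficulty starts in the objective. But the location item is worded differently from its neighbours, and its natural sense is association. If description was meant, the objective should say so.

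A second reply is that a statistical analysis plan, not shown here, could add the denominators. It could, but the point is not missing detail: the protocol itself fixes the set and the statistic, and these cannot answer the question it poses.

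Three further points stand in part.
- The corrected table will be imprecise. Assuming an even spread, with about 12 lesions and 2 events per site, a Wilson 95% interval for 2/12 runs from about 5% to 45%. This argues for collapsed groups and no formal test.
- OCT-arm rates alone do not separate sites where OCT mapping fails from sites that need more stages under any method. That would need the same table for the control arm.
- The items listed as recorded in Figure 1, Outline Protocol, do not include location, but that list is an outline. First-stage margin status is also absent from it, although it is analysed. The omission does not show that location will go unrecorded.

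**Conclusion.** The concern holds and is minor. As written, the location analysis cannot meet its objective, because all the lesions analysed share the same outcome. One and the same planned table fits a risk ratio anywhere from 2.67 to 0.44 in the illustration. Those sizes rest on assumed nasal counts and show the logic; they do not predict the distortion in this trial. The figure of 20 or fewer expected events rests on the protocol's assumed mean of 1.2 in 100 lesions, and the figure of 17 on a geometric stage count as well. One exploratory tertiary item is affected. The other tertiary items and the primary and secondary results are not.

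**What to change.** For the location item only, replace the share among multi-stage lesions with the proportion needing more than one stage within each location, calculated over all OCT-arm lesions. Collapse the eight categories into a few pre-specified groups, give 95% confidence intervals, label the result exploratory and make no formal test. State that location is recorded for every OCT-arm lesion, whatever its number of stages. If the sponsor wants to speak about OCT mapping specifically, the same table for the control arm should be added.

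Alternatively, keep the analysis and reword the objective so that it asks only for the proportion of multi-stage lesions in each anatomical location.

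The cost is one sentence of analysis text plus one recorded item, or one reworded objective. Location is a fixed attribute of the lesion, so neither route needs an extra procedure or a change in sample size.
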